9.4 Data sources

The source of information for the study will be self-reported data collected using a standard questionnaire with closed-ended response choices.

Data will be obtained through questionnaire responses from physicians enrolled in panels from targeted countries. The panels of physicians are convenience samples of physicians derived from multiple sources (e.g., hospital books, medical directories, yellow pages, peer referrals). A stringent sampling procedure for panel member recruitment is in place to target a representative demographic cross section. A rigorous verification process is implemented to confirm potential panellists' practising status. The verification process includes checking physician background data against medical directories. Panel membership will only be finalised once live contact and verification is made with the physician at an office location.

The questionnaire was developed and tested using best practices for instrument development (3). Before study implementation, the questionnaire will be tested through cognitive pretest interviews with physicians in each country.

Cognitive pretest interviewing is a well-established qualitative research methodology used to identify problems with questionnaire items and response options (4). The questionnaire will be tested in local languages to ensure that the introductory material, consent forms, and questionnaire items (question stems and response choices) are culturally appropriate and easily and correctly understood by physicians similar to those who will participate in the study.

Specifically, trained interviewers will ask interview participants to complete the questionnaire while thinking aloud or describing their thought processes as they answer the questionnaire items. Pretest interviewers will use an interview guide that includes probe questions designed to help interviewers understand how each participant interprets and chooses his or her answers for each item in the questionnaire. The pretest interviews are designed to help identify problems with questionnaire items, including the question stems and response choices, and to ensure that participants understand the instructions. The pretest interview data will be used to optimise the language used in the questionnaire prior to fielding the study. Likewise, the cognitive pretest interviews will help identify cultural or translational issues with the questionnaire so that the questionnaire can be modified to meet the individual needs of each country while maintaining comparability across the study.

Cognitive pretesting of the physician questionnaire will be conducted with 25 physicians across the five participating countries who prescribe CPA monotherapy.

9.5 Study size

The study will target the recruitment of a minimum of 600 participating physicians across the 5 countries. Specifically, we will target a minimum of 200 physicians in France and a minimum of 100 physicians each in Germany, Poland, the Netherlands, and Spain. In Poland and the Netherlands, the estimated patient exposure is low, and it may not be feasible to recruit 100 physicians in those countries within the study timeline. If this is the case, a minimum of 60 physicians will be targeted in Poland and the Netherlands and more physicians will be recruited among the other countries to ensure a total of at least 600 participating physicians.

The study will target recruitment based on the following for each country:

- Up to 30% of the total respondents in each country will be general practitioners
- Up to 25% of the total respondents in each country will be urologists or oncologists with a minimum of five of each type (e.g., 10% urologist and 15% oncologist)
- The remaining respondents in each country will be dermatologists, psychiatrists, gynaecologists, and endocrinologists, with a minimum of five physicians each for dermatologists, psychiatrists, and gynaecologists in each country. Given the high prescribing pattern of CPA monotherapy by gynaecologists in France, up to 40% of total respondents in France will be gynaecologists. Efforts will be made to recruit five endocrinologists in each country.

The final sample size for each specialty will ultimately depend upon the actual number of physicians among each specialty who prescribe CPA monotherapy in each country, the availability of eligible physicians on the panels, and the response rates for the survey, which are as yet unknown. Recruitment will be monitored throughout data collection. If recruitment of a particular specialty is slow in one country, then will consult with Bayer to consider modifications to the initial sampling frame and/or target recruitment goals to achieve a diverse sample that is representative of the type of physicians prescribing CPA monotherapy.

Table 2 shows the exact 95% confidence limits assuming various combinations of sample size and correct response percentages (5). For example, if we assume that the total sample of participants can be treated as a simple random sample and that the percentage of correct responses to a yes/no question is 85%, then for a total sample size of 600, the two-sided 95% confidence limits will be 82% to 88%. For the smaller countries, if we assume that the sample of participants in each country can be treated as a simple random sample and that the percentage of correct responses to a yes/no question is 85%, then for a sample size of 60, the two-sided 95% confidence limits will be 73.4% to 92.9%. For the larger countries, if we assume that the percentage of correct responses to a yes/no question is 85%, then for a sample size of 200, the two-sided 95% confidence limits will be 79.3% to 89.6%.

Table 2: Exact 95% Confidence Limits for Various Combinations of Physician Sample Size and Percentage of Correct Responses (5)

Sample Size	Correct Response (%)	Lower 95% Confidence Limit (%)	Upper 95% Confidence Limit (%)
60	80	67.7	89.2
60	85	73.4	92.9
100	80	70.8	87.3
100	85	76.5	91.4
200	80	73.8	85.3
200	85	79.3	89.6
300	80	75.0	84.4
300	85	80.4	88.8
400	80	75.7	83.8
400	85	81.1	88.4
500	80	76.2	83.4
500	85	81.6	88.0
600	80	76.6	83.1
600	85	81.9	87.8

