9.7 Data analysis

All statistical details including calculated variables and proposed format and content of tables will be detailed in the statistical analysis plan (SAP). The SAP will be finalised before study database lock. The SAP will be available upon request.

All analyses will be descriptive in nature, and no hypothesis testing will be performed. Tables displaying the frequency distribution of responses to each individual question will be created. Potentially, summary measures may be developed by combining responses across logical grouping of the survey questions. For example, four true/false questions about similar topics may be combined into a single summary score variable with values that range from 0 to 4 depending on how many of the four questions were answered correctly.

Descriptive tables will be generated for the physicians overall, stratified by specialty and country and other identified variables of interest. Analysis tables will include the frequency and percentage of physicians who select each response to each individual question.

As outlined in Section 9.1.1, the endpoints to be assessed are the percentage of physicians responding correctly to each individual knowledge question. In addition, for knowledge questions with multiple correct responses, derived variables will be created to summarise the number of correct responses selected.

Exact Clopper-Pearson 95% confidence intervals will be reported around the percentage of participants that answer each knowledge question correctly for the overall, by-specialty, and by-country results. The specific tables to be included will be finalised in the analysis plan.

Results from this study will be reviewed qualitatively to identify patterns suggesting that the educational activities have been successful (e.g., consistently high percentages of correct responses across all questions), not successful (e.g., consistently low percentages of correct responses), or partially successful (e.g., high percentages for most responses and low percentages for selected responses). The results for each country will be evaluated and interpreted in the context of the local medical practices and the method and timing of the risk minimisation measures implementation.

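### Section 9.5 gives the n=200 confidence limits for the larger countries in the plural, but only France is planned at 200; Germany and Spain have a minimum of 100 each

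*Protocol*

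**What the plan says.** Section 9.5 sets the sample by country: "a minimum of 200 physicians in France and a minimum of 100 physicians each in Germany, Poland, the Netherlands, and Spain". The overall floor is stated as "The study will target the recruitment of a minimum of 600 participating physicians across the 5 countries". If 100 cannot be reached in the two low-exposure countries, "a minimum of 60 physicians will be targeted in Poland and the Netherlands and more physicians will be recruited among the other countries", so that the total stays at 600 or more.

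The paragraph above Table 2 then gives worked examples at 85% correct. For the smaller countries it reads "then for a sample size of 60, the two-sided 95% confidence limits will be 73.4% to 92.9" per cent. The next sentence begins "For the larger countries, if we assume that the percentage of correct responses to a yes/no question is 85" per cent and continues "then for a sample size of 200, the two-sided 95% confidence limits will be 79.3% to 89.6" per cent. The text has no worked example for n=100, but Table 2 contains that row: 76.5% to 91.4% at 85% correct.

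By-country intervals are a planned output. Section 9.7 says that "Exact Clopper-Pearson 95% confidence intervals will be reported around the percentage of participants that answer each knowledge question correctly", and lists the country results among those covered.

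**The concern.** The worked examples sort the countries into smaller ones at n=60 and larger ones at n=200. The only countries that may drop to 60 are Poland and the Netherlands, so the larger group has to be France, Germany and Spain. Of these, only France has a target of 200. No second country is planned at that size, so the plural cannot be right under the stated targets.

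At stake is what a reader expects of the German and Spanish results. Section 9.7 says each country's results will be evaluated and interpreted, and someone who relies on the prose would expect tighter intervals for these two countries than the planned numbers deliver. The planned minimum of 100 applies to four of the five countries, yet it is the one planned country size with no worked example.

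**Working it through.** **Inputs.** All come from the protocol.
- Two-sided exact (Clopper-Pearson) 95% limits: sections 9.5 and 9.7.
- 85% correct: section 9.5.
- Country minimums of 200 (France) and 100 (each of the other four), fallback of 60 in Poland and the Netherlands, total of at least 600: section 9.5.

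**Formula.** With x = 0.85n correct answers, the lower limit is the 0.025 quantile of Beta(x, n − x + 1) and the upper limit is the 0.975 quantile of Beta(x + 1, n − x).

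**The plan's own figure.** For n=200, x=170: 79.28% to 89.65%, width 10.36 points. This reproduces the stated 79.3% to 89.6%. All 14 rows of Table 2 also reproduce to within 0.1 point.

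**Germany and Spain at the planned minimum.** For n=100, x=85: 76.47% to 91.35%, width 14.89. The ratio of widths is 10.36 / 14.89 = 0.696, so the n=200 interval is 30% narrower than the one these countries would get; equivalently, theirs is 44% wider. The rounded limits in Table 2 give nearly the same: (89.6 − 79.3) / (91.4 − 76.5) = 10.3 / 14.9 = 0.691.

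**How far the fallback can close the gap at a total of 600.** With Poland and the Netherlands at 60 each, 600 − 120 = 480 places remain. France needs at least 200, which leaves at most 280 for Germany and Spain together. Beyond the three minimums (200 + 100 + 100 = 400), 80 places are free.
- Shared in proportion to the minimums: 40 to France, 20 each to Germany and Spain, so n=120.
- All to Germany and Spain, split evenly: 280 / 2 = 140 each.
- All to one of them: 280 − 100 = 180, with the other left at 100.

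| n | x | Exact 95% limits (%) | Width (points) | Shortfall of the n=200 width |
|---|---|---|---|---|
| 200 | 170 | 79.28 to 89.65 | 10.36 | none |
| 100 | 85 | 76.47 to 91.35 | 14.89 | 30% |
| 120 | 102 | 77.33 to 90.86 | 13.53 | 23% |
| 140 | 119 | 77.99 to 90.47 | 12.48 | 17% |
| 180 | 153 | 78.93 to 89.88 | 10.95 | 5% |

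Widths and shortfalls come from unrounded limits, so the last digit can differ from the difference of the printed limits. The shortfall is 1 − 10.36 / width.

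**The case against.** The best defence is that nothing has been miscalculated. The sentence is conditional on a sample size of 200, it sits in a paragraph of examples, it does not name Germany or Spain, and the n=100 row is printed in the table directly below. A careful reader can find the right limits without help. This stands as far as it goes: Table 2 is correct, and the inclusion of Germany and Spain rests on the plural and on the fallback applying only to the other two countries. It does not rescue the label, because the plural is true of no second country under the stated targets.

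It is also fair that the sample sizes are minimums. A reader might argue that three countries at 200 and two at 60 need 3 × 200 + 2 × 60 = 720 physicians, and conclude that 200 in Germany and Spain is impossible. The protocol does not support that: 600 is a floor, and over-recruitment is open. What holds is narrower: at a total of 600, neither country reaches 200. Section 9.9 expects a particularly low response in Germany, which makes large over-recruitment there less likely.

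The consequence is small, and this part of the defence stands in full. Section 9.7 plans descriptive analysis without hypothesis tests. Section 9.9 says most of the analysis will pool the countries and warns about country-specific conclusions. Section 9.7.1 sets no formal threshold and calls 60% correct reassuring; at 85% correct, both lower limits (76.5% and 79.3%) are well above that. The final report will show the intervals actually obtained.

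**Conclusion.** The point holds as a wrong label on a correct figure. The prose in section 9.5 attributes n=200 precision to a group of countries of which only France is planned at 200. For Germany and Spain the stated interval is about 30% too narrow at the planned minimum of 100. The gap falls to about 17% at 140 each, and to 5% for one country at 180 while the other stays at 30%; these lower figures need the full 60/60 fallback, all 80 freed places going to these two countries, and a total of exactly 600. The 30% is therefore the figure at the planned minimum and not an unconditional one. All the percentages assume 85% correct and exact two-sided 95% limits, as in the protocol's example.

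A reader might extend the criticism to specialties, because section 9.7 also promises by-specialty intervals and section 9.5 asks for "with a minimum of five physicians each for dermatologists, psychiatrists, and gynaecologists in each country", with the same minimum for urologists and oncologists: 5 × 5 = 25 across the five countries. That extension is not supported. Section 9.5 states no by-specialty precision, so nothing is misstated. The five-per-country numbers are recruitment targets that the same section allows to be modified, so 25 is not a guaranteed specialty sample size.

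No planned analysis or conclusion changes; this is a minor correction to a stated precision.

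**What to change.** In the paragraph above Table 2 in section 9.5, replace *For the larger countries* with *For France* in the n=200 example, and add: *for Germany and Spain, at the planned minimum of 100, the limits will be 76.5% to 91.4%*. The added figures are already in Table 2, so the table needs no change. The abstract states the sample sizes without this precision example and can stay as it is.

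The cost is one changed phrase and one added clause. Design, recruitment targets and analysis are untouched; the only effect is that the precision stated for two countries becomes less favourable and matches the plan.

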9.6 Data management

A web-based electronic data capture (EDC) system will be used in this study. Information on the EDC system will be available upon request. Detailed information on data management, including procedures for data collection, retrieval, and preparation are given in the Data Management Plan (DMP), which will be available upon request.

For information on quality control, refer to Section 9.8.

9.7 Data analysis

All statistical details including calculated variables and proposed format and content of tables will be detailed in the statistical analysis plan (SAP). The SAP will be finalised before study database lock. The SAP will be available upon request.

All analyses will be descriptive in nature, and no hypothesis testing will be performed. Tables displaying the frequency distribution of responses to each individual question will be created. Potentially, summary measures may be developed by combining responses across logical grouping of the survey questions. For example, four true/false questions about similar topics may be combined into a single summary score variable with values that range from 0 to 4 depending on how many of the four questions were answered correctly.

Descriptive tables will be generated for the physicians overall, stratified by specialty and country and other identified variables of interest. Analysis tables will include the frequency and percentage of physicians who select each response to each individual question.

As outlined in Section 9.1.1, the endpoints to be assessed are the percentage of physicians responding correctly to each individual knowledge question. In addition, for knowledge questions with multiple correct responses, derived variables will be created to summarise the number of correct responses selected.

Exact Clopper-Pearson 95% confidence intervals will be reported around the percentage of participants that answer each knowledge question correctly for the overall, by-specialty, and by-country results. The specific tables to be included will be finalised in the analysis plan.

Results from this study will be reviewed qualitatively to identify patterns suggesting that the educational activities have been successful (e.g., consistently high percentages of correct responses across all questions), not successful (e.g., consistently low percentages of correct responses), or partially successful (e.g., high percentages for most responses and low percentages for selected responses). The results for each country will be evaluated and interpreted in the context of the local medical practices and the method and timing of the risk minimisation measures implementation.

Survey results will be stratified on selected variables (e.g., age, gender, practice setting, type of physician) to see whether an imbalance of the characteristics of responders versus nonresponders could cause a bias in the overall study results. An imbalance would lead to a bias in the knowledge results only if there were differences in knowledge between the different levels of the imbalanced characteristic. For example, if the study sample includes a much higher percentage of males than that of the overall population of each specialty, an examination of knowledge by gender will identify whether this imbalance would cause a bias in the overall results. If the stratified results show that knowledge is similar by gender, the imbalance should not bias the overall results.

In addition to the stratification performed to assess responder bias, the overall results tables of the knowledge questions will be stratified by other variables (e.g., number of years treating patients, time between when the physicians reviewed the prescriber guide and took the survey, average number of prescriptions of CPA monotherapy each month) to identify whether any of these variables have an impact on knowledge.

Typically, questionnaire data are mostly complete, and each question will be analysed individually among those participants who respond. The analysis population will consist of respondents who were eligible for the study, provided informed consent, and completed at least one of the knowledge questions. No imputation of missing data will be performed.

All analyses will be performed using SAS version 9.4 (or higher) statistical software. Programmes, logs, and output will be reviewed for accuracy according to relevant standard operating procedures.

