The primary endpoints to be assessed are the percentage of physicians responding correctly to each individual knowledge question.

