9.3 Variables

A questionnaire will be developed to elicit responses measuring physician knowledge and understanding of the key information included in the revised SmPC and DHPC for CPA monotherapy. This questionnaire will contain closed-ended questions (e.g., multiple choice, true/false) with no free-text response fields, eliciting responses measuring physician knowledge and understanding of the key information in the revised SmPC and DHPC for CPA monotherapy. The physician questionnaire will include items in the following content areas:

- Approved indications of CPA monotherapy
- Occurrence of meningiomas in association with CPA monotherapy
- Contraindications relevant to meningioma
- Signs and symptoms of meningioma
- Restriction of the indication to second-line treatment

- Approved dosing (i.e., treatment should be prescribed for the shortest possible time and with the lowest effective dose)
- Risk factors associated with meningioma (i.e., risk increases with increasing cumulative doses)

The questionnaire will also include the following items to investigate physician receipt and use of the DHPC and revised SmPC:

- Receipt and review of the DHPC and SmPC
- Estimated time between the physicians' review of the DHPC and SmPC and completion of the survey

In addition, the physician questionnaire will include queries on the following items to characterise the physicians and their practices:

- Physicians' practice setting
- Average number of CPA monotherapy prescriptions each month
- Years in practice
- Gender
- Age

Because approved indications and dosing vary by country, adaptations may be made to the questionnaire to ensure that it is specific and applicable to the country where it is being administered.

The questionnaire is anticipated to take 10 to 15 minutes to complete and will be administered in the local language for each country. The questionnaire will be administered electronically and programmed so that respondents will not be able to move backward in the survey to change their answers to previous questions.

The draft version of the questionnaire is included in Annex 3.

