9.7.1 Statistical considerations

No *a priori* thresholds of correct responses to the questions are established as targets for this study given the variability in prescriber specialty and indication. However, having a minimum of 60% of respondents selecting the correct response for each question would be considered reassuring regarding physician awareness and knowledge of the product's safety information. In a review of survey-based studies evaluating the effectiveness of risk minimisation measures in Europe, most participants responding correctly was considered a successful result in 9 of 11 surveys registered in the EU PAS Register (6).

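### The supplementary count for multi-answer knowledge questions takes no account of wrong options ticked, so indiscriminate ticking can reach the maximum

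*Protocol*

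**What the plan says.** Section 9.1.1 of the protocol sets the endpoint: "The primary endpoints to be assessed are the percentage of physicians responding correctly to each individual knowledge question". Section 9.7 repeats it, attaches exact Clopper-Pearson intervals to it, and then adds a second summary for one type of item: "for knowledge questions with multiple correct responses, derived variables will be created to summarise the number of correct responses selected". No other summary specific to multi-answer items is named.

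Three further statements bear on the point:

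- On tables, section 9.7 says: "Analysis tables will include the frequency and percentage of physicians who select each response to each individual question".
- On where the detail belongs, section 9.7 says: "All statistical details including calculated variables and proposed format and content of tables will be detailed in the statistical analysis plan (SAP").
- On item format, section 9.3 says: "This questionnaire will contain closed-ended questions (e.g., multiple choice, true/false) with no free-text response fields". One of its content areas is "Signs and symptoms of meningioma". The numbers of correct and wrong options per item are not given; the questionnaire is listed in Annex 1 as a stand-alone document.

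Section 9.7.1 sets no formal target but remarks that "having a minimum of 60% of respondents selecting the correct response for each question would be considered reassuring".

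**The concern.** A multi-answer item tests two things: recognising what is true and rejecting what is false. A count of correct options ticked measures only the first. It rises with willingness to tick as well as with knowledge, and it cannot fall when a wrong option is ticked. If the symptom item, for example, is in tick-all-that-apply form, a physician who ticks the whole list looks fully informed on this variable.

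The study judges success qualitatively, from patterns of high or low correct responses. A summary that can be high without discrimination between true and false options could therefore make knowledge on those items look better than it is.

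**Working it through.** **The plan's own figure.** Table 2 gives exact limits for n = 600 and 85% correct as 81.9% to 87.8%. With x = 0.85 × 600 = 510, the lower limit is the 0.025 quantile of Beta(x, n − x + 1) = Beta(510, 91), and the upper limit is the 0.975 quantile of Beta(x + 1, n − x) = Beta(511, 90). The results are 81.89% and 87.76%. All 14 rows of Table 2 reproduce to rounding. They concern the percent-correct endpoint and are untouched by this point.

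**What the count does with an over-ticker.** Let an item have k correct and w wrong options, with no limit on selections. A physician who ticks everything selects all k correct options, so the count is k of k whatever w is. The documents do not give k and w, so the values below are assumptions. Each row scores a physician who ticks everything.

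| k, w | Correct options ticked | Options classified correctly, k/(k + w) | Exact match |
|---|---|---|---|
| 3, 2 | 3/3 | 3/5 | no |
| 4, 2 | 4/4 | 4/6 | no |
| 5, 3 | 5/5 | 5/8 | no |
| 6, 3 | 6/6 | 6/9 | no |

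**Effect on the share at the maximum.** Let a share t know the full answer and a different share q tick everything, with nobody else at the maximum. The share at the maximum count is t + q, against t under exact match. With assumed t = 50% and q = 5%, 10% or 20%, this is 55%, 60% or 70% against 50%. The overstatement equals the assumed q, so this shows how the error scales and does not estimate it.

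**Whether the per-option tables repair it.** Take an assumed item with k = 3 and w = 2 and 100 physicians, all of whom tick the three correct options.

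- Case A: 80 tick nothing else and 20 tick both wrong options.
- Case B: 60 tick nothing else, 20 also tick the first wrong option only, and 20 also tick the second only.

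In both cases each correct option shows 100%, each wrong option shows 20%, and 100% of physicians have the maximum count of 3. Yet 80% have an error-free answer in A and 60% in B, and 20 physicians ticked everything in A against none in B. The two promised outputs are identical, so they cannot separate the cases. The number of options classified correctly does: in A, 80 physicians score 5/5 and 20 score 3/5; in B, 60 score 5/5 and 40 score 4/5.

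**Why the rule for an item being answered correctly deserves the same care.** Assume k = 6, w = 3, and each option classified correctly by 85% independently. At least one correct option ticked: 1 − 0.15^6, about 100%. All six correct options ticked: 0.85^6, about 38%. All six ticked and no wrong one: 0.85^9, about 23%. Real answers are correlated, which would narrow these gaps, but the choice of rule can put the same data on either side of the 60% remark.

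**The case against.** The strongest answer is that the count is only an extra. Its sentence opens by presenting it as an addition to the percent-correct endpoint, and the intervals and the 60% remark attach to that endpoint. A reader might infer that multi-answer questions are scored for the primary endpoint by this count, and hence that the endpoint is inflated. The documents do not support that: nowhere is the count used to decide whether a question was answered correctly.

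A reader might also infer that the missing definition of a correct answer for these items is itself a defect. That does not follow either. Calculated variables are expressly assigned to the SAP, which is not shown and may define one. It may also add a variable for wrong selections; the protocol does not say they will be disregarded throughout the analysis.

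Wrong ticks are not hidden, since every response option is tabulated. And over-ticking may be impossible or harmless: a true/false grid, a cap on selections or an item with no wrong options would remove the problem.

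All of this stands, and it limits the point to the supplementary variable. Two things survive. The variable is stated, and on its wording it records correct ticks only. And the option tables are marginal percentages, so they do not show whether physicians at the maximum count also ticked wrong options.

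**Conclusion.** The point holds as a minor, inexpensive improvement to a supplementary descriptive variable. As worded, the count gives a physician who ticks everything the same maximum as one with complete knowledge, provided that the item has wrong options and allows unlimited selections. Both conditions are assumptions until the questionnaire is checked. The size is unknown; the percentages worked above rest on assumed items and assumed shares of over-tickers. No figure in the protocol is wrong, and inflation of the primary endpoint is not shown.

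**What to change.** In section 9.7, or in the SAP where it defines this variable, do one of the following for items with several correct options:

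- replace the count with the number of options each physician classifies correctly, that is, correct ones ticked plus incorrect ones left blank; or
- keep the count and report beside it, per physician, the number of incorrect options selected, preferably cross-tabulated with the count.

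Also make sure that the rule for counting such an item as answered correctly takes incorrect selections into account, and fix it before data collection. Exact match (all correct options and no incorrect one) is one possible rule. It is strict, since it fails a physician who misses one of many symptoms, so another rule can be defended if it is stated in advance. On timing, the abstract has the analysis plan developed before data collection starts, whereas section 9.7 requires the SAP to be final only before database lock; for this rule the earlier date should apply.

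The cost is a sentence or two of text and minor extra programming. The downside is that reported scores on these items will be slightly lower. Nothing changes in the sample size, the questionnaire or Table 2.
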